#### **4.2.4.3 Additional efficacy variables**

Unless otherwise specified, the following variables will use data collected during the whole study period using on-treatment analysis.

### **Analyses for COPD Exacerbations**

The rate of COPD exacerbations per patient per year (any, and moderate or severe) and rate of hospitalizations due to COPD exacerbations per patient per year will be analyzed using a Negative Binomial regression model (or Poisson regression model taking overdispersion into account for analyses that Negative Binomial regression does not converge) similar to the primary analysis of the primary efficacy variable. The exposure time will be re-calculated based on the last data collection during the whole study period.

The number of patients with at least one COPD exacerbation (any, mild, moderate, severe, and moderate or severe) will be analyzed based on a logistic regression model with treatment group, baseline ICS use, baseline COPD severity, history of at least one exacerbation in the past year, and smoking status as factors. The estimated treatment effect (i.e., the odds ratio of aclidinium over placebo), corresponding 95% CI, and two-sided p-value for the odds ratio will be presented. The model is as follows:

*Response (Yes=1/No=0) = treatment group + baseline ICS use + baseline COPD severity + history of at least one exacerbation in the past year + smoking status*

Time (in days) to first COPD exacerbation (any, and moderate or severe), time (in days) to second COPD exacerbation (any, and moderate or severe), time (in days) to third COPD exacerbation (any, and moderate or severe), time (in days) to first hospitalization due to COPD exacerbation, and time (in days) to withdrawal of the double-blind IP due to COPD exacerbation will be analyzed by means of Kaplan-Meier estimators and Cox Proportional Hazards model. The estimates of the hazard ratio comparing aclidinium with placebo will be derived using the Cox proportional hazard model for the time in terms of the number of days served as a response variable and treatment group, baseline ICS use, baseline COPD severity, history of at least one exacerbation in the past year, and smoking status as factors. The hazard ratio (aclidinium over placebo), corresponding 95% CI, and two-sided p-value for the hazard ratio will be presented. The model is as follows:

*Survival time = treatment group + baseline ICS use + baseline COPD severity + history of at least one exacerbation in the past year + smoking status*

In addition, the Kaplan-Meier survival curves will be displayed for each treatment group along with p-value for differences (aclidinium over placebo) based on the Log-Rank test stratified by baseline COPD severity and smoking status.

The durations of COPD exacerbation (any, and moderate or severe; in days) will be summarized descriptively for only the patients who had exacerbations during the treatment period.

Number of days hospitalized due to COPD exacerbations will be summarized for only the patients who had exacerbations during the treatment period. The descriptive statistics of number of days hospitalization due to COPD exacerbations will be summarized by unit type (any, hospitalization unit, intensive care unit, emergency room).

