## 1.2 Study design

This is a Phase IV, multicenter, randomized, double-blind, placebo-controlled, parallel-group study evaluating the effect of Acclidinium Bromide (a long-acting muscarinic antagonist delivered by the Pressair® dry powder inhalation [DPI] device) compared with placebo on long-term CV safety and COPD exacerbations in outpatients at least 40 years of age who have been diagnosed with moderate to very severe COPD (postbronchodilator % predicted forced expiratory volume in 1 second [FEV1] < 80% and FEV1/forced vital capacity [FVC] ratio < 70%) and a history of CV or cerebrovascular disease and/or significant CV risk factors.

Note: in this document

1. The term “double-blind treatment period” applies to the following 2 scenarios:
  - When used in “maximum of 36-months double-blind treatment period”
  - When used for patients who completed 36-months treatment (completer)
2. The term “during the treatment period” refers to on-treatment period.
3. The term “during the whole study period” refers to both on-treatment and off-treatment (post-treatment follow-up) periods.

The study consists of two-week washout/run-in period (for patients on a long-acting muscarinic antagonist [LAMA]) followed by a maximum of 36-month double-blind treatment period.

Signed informed consent form (ICF) from the patient or the patient’s legally authorized representative will be obtained before any study-related procedures are begun. All patients will be assigned a patient identification (PID) number via the interactive web response system (IWRS). Patients meeting the entry criteria for this study will be randomized (1:1) to acclidinium bromide 400 µg (abbreviated as acclidinium hereafter) twice a day (BID) or placebo BID. This study will conclude when 122 patients have experienced an adjudicated MACE.

Patients who prematurely discontinue investigational product (IP) will participate in a post-treatment follow-up period. The follow-up period will include on-site visits and telephone visits to collect MACE, COPD exacerbations, concomitant medications, and SAEs for the remainder of the study duration.

An independent Data Safety Monitoring Board (DSMB) will be established for this study. The DSMB will periodically monitor and review relevant clinical safety data, including adjudicated MACE.

Patients will be assessed according to the Schedule of Evaluations (See Section 2 of the clinical study protocol [CSP]).

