### 3.1.7 Derived variables

#### 3.1.7.1 Rate of event

The rate of event per patient per year during a given period (e.g., during the first year of treatment) is calculated as the sum of all available events in that period divided by the sum of all patients follow-up time in that period, i.e.,  $\frac{\sum_{i=1}^n e_i}{\sum_{i=1}^n t_i}$ , where  $e_i$  is the number of event in patient  $i$  and  $t_i$  is the follow-up time in patient  $i$ . The follow-up time in patient  $i$ ,  $t_i$ , is calculated as  $d_i/365.25$ , where  $d_i$  is the number of days patient  $i$  exposed, calculated as (*follow-up date – randomization date + 1*).

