### **3.4 Additional efficacy variables**

#### **3.4.1 COPD exacerbation variables**

The following COPD exacerbation variables use data collected during the whole study period. Maximum follow-up time for a patient is approximately 36 months.

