##### **3.4.1.1 Rate of moderate or severe COPD exacerbations per patient per year**

For the production of summary statistics, the rate of moderate or severe COPD exacerbation per patient per year is calculated by applying the following in the general formula defined in Section 3.1.7.1.

- Event is moderate or severe COPD exacerbation
- Period refers to the whole study period

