#### **3.4.1.10 Time to first hospitalization due to COPD exacerbations**

Time (in days) to first hospitalization due to COPD exacerbations is calculated by applying the following in the general formula defined in Section 3.1.7.3.

- Event is hospitalization due to COPD exacerbation
- Period refers to the whole study period

For patients who do not experience a hospitalization during the study, date of first hospitalization due to COPD exacerbation will be censored at the last dose date (or study closure date for patients who did not discontinue from study treatment). For patients who experience a hospitalization due to reasons other than COPD exacerbation during the study, patients will be censored at the date of first hospitalization (due to reasons other than COPD exacerbation).

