The on-study analysis is defined as all events that occurred while the patient was in the study, irrespective of treatment exposure (i.e., this includes all events that occurred during which the patient was on treatment or off treatment). The on-treatment analysis is defined as only events that occurred while the patient has received at least one dose of study double-blind IP during the treatment period excluding off treatment period/post treatment follow-up (PTFU) period.

The status of patients off treatment during the study period is referred to as the PTFU period.

**Handling professional/duplicate patients.** Professional patients are individuals who, in violation of protocol entrance criteria and enter into the same study more than once and/or enter into more than one study at the same or in close succession.

Unless otherwise stated, the first incidence of patient entering trial is used in analysis and summary. All data is listed for transparency, with flags for duplicate patients to ensure clarity which records are in/out of the analysis.

For handling of AEs, if a patient is on same treatment throughout (across all incidences), include all data in the analysis. If patient is on different treatments (i.e., different randomised treatment received at the second incidence vs the first incidence), the first incidence of patient entering trial is used in analysis.

**Handling data from patients with missing investigator signatures.** These patients will be excluded from the FAS and would be included in screened and randomized patient population.

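### Whole-study exacerbation and hospitalization rates: the SAP takes events on treatment but, read literally, runs exposure into post-treatment follow-up

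*SAP*

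**What the plan says.** Section 4.2.4.3 opens by stating that, unless otherwise specified, "the following variables will use data collected during the whole study period using on-treatment analysis". Its subsection on COPD exacerbations then describes a negative binomial model for the rates of any exacerbation, of moderate or severe exacerbation and of hospitalization. The model is to resemble the primary analysis, with this instruction for the offset: "The exposure time will be re-calculated based on the last data collection during the whole study period".

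The two terms are defined elsewhere:
- Section 1.2, in a note that applies to the whole document, says that the whole study period "refers to both on-treatment and off-treatment (post-treatment follow-up) periods".
- Section 4.1 restricts on-treatment analysis to events "during the treatment period excluding off treatment period/post treatment follow-up (PTFU) period".

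The variable definitions carry no on-treatment limit. Section 3.4.1 begins "The following COPD exacerbation variables use data collected during the whole study period", and Sections 3.4.1.1, 3.4.1.2 and 3.4.1.8 each repeat "Period refers to the whole study period". The general rate formula in Section 3.1.7.1 counts days as "follow-up date – randomization date + 1" and does not define the follow-up date.

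**The concern.** A rate needs its events and its person-time to come from the same window. Here the event rule stops at discontinuation of investigational product (IP), while the offset rule, under the SAP's own definition, continues to the last data collection in post-treatment follow-up. Section 1.2 says that exacerbations are collected during that follow-up. For a patient who stops IP and enters it, the last data collection therefore falls after the last dose.

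A programmer who followed each sentence as written would divide on-treatment events by on-treatment plus off-treatment time. Annual rates would be understated in both arms and could not be compared with the first-year rates. The treatment comparison would also shift if the arms discontinued IP at different rates.

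**Working it through.** **1. The passages side by side.** Three readings are open.
- (a) Each sentence as written: on-treatment events over on-treatment plus off-treatment time. The windows do not match.
- (b) The Section 1.2 definition applied to events and time alike. The windows match, but this contradicts the on-treatment label in Section 4.2.4.3.
- (c) *Whole study period* meaning only *not capped at one year*. Events and time both end at IP discontinuation and match, but this departs from Section 1.2.

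Only (a) distorts the rates, so only (a) needs sizing.

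**2. The nearest figure the plan states.** The SAP gives no figure for the whole-study rates. Section 1.3.2 gives about 89% power for the first-year rate.
- Inputs: 2,000 per arm, placebo rate 0.8, rate ratio 0.86 (so 0.8 × 0.86 = 0.688), k = 0.67, 30% discontinuation in year 1, two-sided 0.05.
- Mean exposure with exponential discontinuation: (1 − 0.70)/(−ln 0.70) = 0.841 year.
- Variance of the log rate ratio: [(1/(0.841 × 0.8) + 0.67) + (1/(0.841 × 0.688) + 0.67)]/2,000 = 0.00228.
- Power: Φ(0.1508/√0.00228 − 1.96) = 88.5%, which agrees with the SAP.

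This match uses person-time that ends at treatment discontinuation.

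**3. Size under reading (a).** From Section 1.3.1: 40% treatment discontinuation and 20% study discontinuation at year 2, exponential; 4,000 patients; 6,500 patient-years. From Section 1.2: a 36-month maximum.
- Hazards: IP −ln(0.60)/2 = 0.2554 per year; study −ln(0.80)/2 = 0.1116 per year.
- Mean time over a potential follow-up T: (1 − e^(−hT))/h.
- Reported rate = true rate × on-treatment time / on-study time.

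If every patient is scheduled for 36 months, mean on-treatment time is 2.096 years and mean on-study time 2.550 years. The ratio is 2.096/2.550 = 0.822.

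The study is event-driven, so many patients may have less than 36 months. Accrual is assumed uniform over 1 or 3 years, follow-up is capped at 3 years, and the closure time is solved so that total time equals 6,500 patient-years. The SAP words that total as treatment time; both interpretations are shown.

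| Scenario | Closure (y) | On-treatment PY | On-study PY | Rate too low by | True 0.80 reported as |
|---|---|---|---|---|---|
| 6,500 = study time, accrual 1 y | 2.30 | 5,739 | 6,500 | 11.7% | 0.71 |
| 6,500 = study time, accrual 3 y | 3.35 | 5,626 | 6,500 | 13.4% | 0.69 |
| 6,500 = treatment time, accrual 1 y | 2.61 | 6,500 | 7,506 | 13.4% | 0.69 |
| 6,500 = treatment time, accrual 3 y | 3.77 | 6,500 | 7,614 | 14.6% | 0.68 |
| All scheduled for 36 months | – | 8,382 | 10,198 | 17.8% | 0.66 |

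**4. Effect on the rate ratio under reading (a).** With on-study time equal in both arms, the reported ratio is 0.86 × aclidinium on-treatment time / placebo on-treatment time. Equal discontinuation leaves it at 0.86. The SAP gives no arm-specific rates, so the following splits at year 2 are illustrations only.

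| Placebo vs aclidinium | Four accrual scenarios | 36 months |
|---|---|---|
| 42% vs 38% | 0.885–0.891 | 0.898 |
| 38% vs 42% | 0.830–0.836 | 0.823 |
| 45% vs 35% | 0.923–0.939 | 0.959 |
| 35% vs 45% | 0.787–0.801 | 0.771 |

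The direction depends on which arm stops more. Time spent in exacerbation is not subtracted in any of these figures.

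**The case against.** The best defence is that reading (c) is what the authors meant, and much of the SAP supports it:
- Section 4.2.4.1 lists descriptive summaries in a two-by-two layout: on-treatment and on-study, each for the first year and for the whole study period. There the period is a horizon and the label is the filter. Section 4.2.4.3 uses the same pairing.
- The sentence before the offset instruction makes the model similar to the primary analysis, where the windows do match. Recalculating exposure may then mean only lifting the one-year cap.
- Section 4.2.3.1 computes exposure from first to last dose, and Section 3.1.7.1 speaks of days exposed.
- Section 3.4.1.10 defines time to first hospitalization over the same whole study period, yet patients without a hospitalization "will be censored at the last dose date (or study closure date for patients who did not discontinue from study treatment".

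This stands as evidence of likely intent, but it does not settle the text. Section 1.2 defines the term the other way for the whole document. Section 4.1 defines on-treatment analysis through events and is silent on person-time. The cut at IP discontinuation in Section 3.1.2 covers time-to-event analyses only. The resemblance to the primary analysis is followed at once by a sentence that changes the exposure, which is the element in question. Matching windows cannot be presumed either: Section 4.2.5.3 reports incidence per 1,000 patient-years of IP exposure for on-study as well as on-treatment MACE.

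It is also fair to object that the shifted rate ratios come entirely from assumed differences between arms. That objection stands.

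**Conclusion.** The point holds as a conflict in wording that should be resolved. One literal reading gives annual rates about 12–18% too low in both arms. That range rests on the SAP's planning discontinuation rates, exponential discontinuation independent of exacerbations, a constant event rate, and assumed accrual. Under the other two readings there is no dilution.

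A reader might infer more, in three ways that the SAP does not support:
- *That a mismatched analysis will be run.* The layout in Section 4.2.4.1 and the reference to the primary analysis make matching windows the likelier intent.
- *That the treatment comparison is biased.* The ratio stays at 0.86 with equal discontinuation, and nothing in the SAP says the arms will differ.
- *That the main conclusions are at risk.* Under Section 4.2.4, only the primary and secondary efficacy variables are in the testing sequence. The first-year primary analysis has matching windows, and the secondary efficacy analysis uses the same model. The MACE analyses do not use this offset.

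**What to change.** 1. In Section 4.2.4.3, replace the exposure sentence with: *Events and exposure use the same window, not capped at one year. On-treatment analyses count events and exposure up to IP discontinuation. On-study analyses count events and follow-up to the applicable on-study censoring date in Section 3.1.2. Time in exacerbation is subtracted as in the primary analysis.*
2. In Section 3.1.7.1, define the follow-up date as the earlier of that date and the end of the stated period (one year for Sections 3.2 and 3.3).
3. In Sections 3.4.1, 3.4.1.1, 3.4.1.2 and 3.4.1.8 and the opening of 4.2.4.3, state that the whole study period is the time horizon and that the on-treatment or on-study label sets the window, so that these sections no longer clash with Section 1.2.

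The on-study rule should point to Section 3.1.2 rather than use last contact for everyone. Section 3.1.2 ends follow-up at the end-of-treatment visit for completers and patients still on treatment, and at the withdrawal date for those who withdraw consent.

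The cost is a few wording changes, with no new data, model or test.

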#### **3.1.6 Definition of COPD exacerbations**

The onset and end of a COPD exacerbation is defined by the investigators in their assessment of patient symptoms and initiation/finalization of treatment (as defined below for the severity of exacerbation), and recorded on COPD Exacerbation page of electronic case report forms (eCRFs).

The severity of a COPD exacerbation is assessed according to the following scale:

- Mild: Increase in COPD symptoms (e.g., dyspnea, cough, sputum volume, sputum purulence) during at least 2 consecutive days, managed by the patient at home by increasing short-acting bronchodilator and/or inhaled corticosteroid (ICS) use
- Moderate: Increase in COPD symptoms (e.g., dyspnea, cough, sputum volume, sputum purulence) during at least 2 consecutive days that does not lead to hospitalization but is treated with antibiotics and/or systemic corticosteroids

- Severe: Increase in COPD symptoms (e.g., dyspnea, cough, sputum volume, sputum purulence) during at least 2 consecutive days that leads to hospitalization (overnight stay at hospital or emergency room) or death

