#### **3.4.1.6 Time to COPD exacerbation**

- Time to first COPD exacerbation

Time to first COPD exacerbation is calculated by applying the following in the general formula defined in Section 3.1.7.3.

- Event is mild, moderate, or severe COPD exacerbation
- Period refers to the whole study period

For patients who do not experience a COPD exacerbation during the study, start date of the first COPD exacerbation will be censored per general censoring rules described in Section 3.1.2, i.e., the event in question refers to a COPD exacerbation.

- Time to first moderate or severe COPD exacerbation during the first year of treatment

Time to first moderate or severe COPD exacerbation during the first year of treatment is similarly calculated and censored as time to first COPD exacerbation, by considering moderate or severe COPD during the first year of treatment only, i.e., patients will be censored on the date of IP discontinuation or at the end of the first year, whichever is earlier.

- Time to first moderate or severe COPD exacerbation

Time to first moderate or severe COPD exacerbation is similarly calculated and censored as time to first COPD exacerbation, by considering moderate or severe COPD only.

- Time to second COPD exacerbation

Time to second COPD exacerbation is calculated as follows:

*Start Date of the second COPD exacerbation – Date of randomization + 1.*

Time to second COPD exacerbation will be analyzed in patients who experience at least one COPD exacerbation. For patients who experience < 2 COPD exacerbations during the study, start date of the second COPD exacerbation will be censored per general censoring rules described in Section 3.1.2, i.e., the event in question refers to the second COPD exacerbation.

- Time to second moderate or severe COPD exacerbation

Time to second moderate or severe COPD exacerbation is similarly calculated and censored as time to second COPD exacerbation, by considering moderate or severe COPD only.

- Time to third COPD exacerbation

Time to third COPD exacerbation is calculated as follows:

*Start Date of the third COPD exacerbation – Date of randomization + 1.*

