#### **3.4.1.7 Time to Withdrawal from the double-blind IP due to COPD exacerbation**

Time (in days) to withdrawal from the double-blind IP due to COPD exacerbation is calculated as follows:

*Date of withdrawal from the double-blind IP due to COPD exacerbation – Date of randomization + 1.*

- For patients who do not withdraw from the double-blind IP, date of withdrawal from the double-blind IP due to COPD exacerbation will be censored at the last dose date.
- For patients who withdraw from the double-blind IP due to reasons other than COPD exacerbation, patients will be censored at the date of withdrawal from the double-blind IP (due to reasons other than COPD exacerbation).

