If the Negative Binomial regression model does not converge, the Poisson regression model with robust variance estimate using sandwich method will be applied. A scale parameter will be included to take overdispersion into account in fitting Poisson regression model. This would be a similar SAS GENMOD model to the one used for the Negative Binomial, but will specify Poisson as the distribution and include a scale parameter (DSCALE).

The primary analysis on the primary efficacy endpoint will be based on on-treatment analysis. For those patients who prematurely discontinue IP during the first year of treatment and have follow-up assessments, the primary analysis described above will be based on the data (events) collected before treatment discontinuation.

The secondary analysis on the primary efficacy endpoint will be based on on-study analysis using the same model as for the primary analyses of the primary efficacy endpoint. For those patients who prematurely discontinue IP during the first year of treatment and have follow-up assessments, the secondary analysis will include the events collected during the PTFU period up to one year.

The individual exacerbation criteria (use of systemic corticosteroids, use of antibiotics, and inpatient hospitalization due to COPD) will also be analysed using the same method as the primary analysis for on-treatment analysis during the first year of treatment, and will be summarized descriptively for on-study analysis over the whole study period.

The frequency of events and descriptive statistics of moderate or severe COPD exacerbations will also be provided by analysis method and period:

- On-treatment analysis during the first year of treatment
- On-study analysis during the first year of treatment
- On-treatment analysis over the whole study period
- On-study analysis over the whole study period.

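### The on-treatment logistic comparison of patients with at least one exacerbation ignores time on drug, and for the mild and the moderate categories it is the only planned whole-study between-arm comparison

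*SAP*

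**What the plan says.** Section 4.2.4.3 opens with a default: unless otherwise specified, "the following variables will use data collected during the whole study period using on-treatment analysis". Section 4.1 defines on-treatment so that events in post-treatment follow-up are excluded. Under Analyses for COPD Exacerbations, the count of patients having one or more events, taken for five severity groupings that include mild and moderate as separate entries, "will be analyzed based on a logistic regression model with treatment group, baseline ICS use, baseline COPD severity" and two further baseline factors. The written model has a Yes/No response, treatment and four baseline factors. It has no exposure term, offset or fixed time point. An odds ratio, 95% CI and two-sided p-value are to be presented.

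The neighbouring analyses do use time on drug:

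- The rate models follow the primary model, with log exposure as offset. They cover any, moderate or severe, and hospitalization.
- The Cox and Kaplan-Meier analyses censor at IP discontinuation (section 3.1.2). They cover "Time (in days) to first COPD exacerbation (any, and moderate or severe"), the second and third such events, and first hospitalization.
- Section 3.4.1.6 adds "Time to first moderate or severe COPD exacerbation during the first year of treatment".
- Section 4.2.4.1 states: "The individual exacerbation criteria (use of systemic corticosteroids, use of antibiotics, and inpatient hospitalization due to COPD) will also be analysed". These criteria are modelled for the first year only and are descriptive over the whole study.

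The severe category is nearly covered by the hospitalization analyses, since section 3.1.6 defines it as an event "that leads to hospitalization (overnight stay at hospital or emergency room) or death". No rate or time-to-event model is planned for the mild or the moderate category by itself.

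**The concern.** A patient who stops IP after a few weeks without an event counts as No, exactly like a patient treated event-free until study closure. Time on drug will vary widely: section 1.3.1 assumes 40% treatment discontinuation at year 2, and section 3.1.1 closes the study at 122 patients with MACE.

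The proportion with an event while on drug is a fair description. As a between-arm odds ratio with a p-value it is harder to read, because the arm that stays on drug longer has more time to record an event. If that arm is aclidinium, a real benefit is diluted. If it is placebo, a benefit can appear where there is none.

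For a single severity there is a second route. A patient who stops after an exacerbation of another severity leaves before a mild or moderate event can be seen. The SAP expects some withdrawals of this kind: "Time (in days) to withdrawal from the double-blind IP due to COPD exacerbation is calculated as follows".

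For any and for moderate or severe events, the rate and Cox results stand next to the odds ratio. For the mild and the moderate categories the reader has nothing else over the whole study.

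**Working it through.** **Reproducing the SAP's own figures.** With n = 2,000 per arm, placebo rate 0.8, rate ratio 0.86, k = 0.67 and 30% exponential first-year discontinuation (section 1.3.2), mean exposure is (1 - 0.70)/0.3567 = 0.841 years. The variance of the log rate ratio is [1/(0.8 × 0.841) + 1/(0.688 × 0.841) + 2 × 0.67]/2,000 = 0.00228. So z = 0.1508/0.0477 = 3.16 and power is 88.5%, against about 89% stated. The MACE target also reproduces: 4 × (1.960 + 1.282)²/(ln 1.8)² = 121.7, i.e. 122.

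**Inputs for the odds ratio.** From the SAP: rate 0.8, k 0.67, pooled 40% off drug and 20% out of study at year 2, 1.9 MACE per 100 patient-years, a 36-month maximum and closure at 122 MACE. Assumed: any split of stopping between arms, stopping independent of exacerbations, uniform accrual over 1, 2 or 3 years, and any rate for a single severity. Model covariates are left out.

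**Step 1, closure.** The study-discontinuation hazard is -ln(0.80)/2 = 0.1116. Let G(t) be the share of patients whose entry date allows t years before closure. Solving 4,000 × ∫ 0.019 exp(-(0.019 + 0.1116)t) G(t) dt = 122 over 0 to 3 years puts closure at 2.31, 2.82 or 3.37 years. On-treatment time is then 5,762, 5,723 or 5,666 patient-years. Of the No patients, 44-49% would have stopped IP early.

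**Step 2, probability of Yes.** First-event survival is S(t) = (1 + 0.67λt)^(-1/0.67), with density f(t). The stopping hazard is h = -ln(1 - p)/2, where p is the proportion off drug at year 2: 0.223 for 36% and 0.290 for 44%. P(Yes) = ∫ f(t) exp(-ht) G(t) dt.

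**Step 3, results.** Splits are aclidinium/placebo. Rejection is the chance that a two-sided 0.05 Wald test of the log odds ratio is significant.

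| λ (placebo) | True rate ratio | Off drug at year 2 | OR | Rejection |
|---|---|---|---|---|
| 0.8 | 1 | 40/40% | 1.00 | 5% |
| 0.8 | 1 | 38/42% | 1.04 | 10% |
| 0.8 | 1 | 36/44% | 1.09 | 26-27% |
| 0.8 | 1 | 44/36% | 0.92 | 26-27% |
| 0.2-0.6 | 1 | 36/44% | 1.07-1.08 | 14-24% |
| 0.8 | 0.86 | 40/40% | 0.86-0.87 | 63-67% |
| 0.8 | 0.86 | 36/44% | 0.94 | 17-19% |

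Worked line (2-year accrual, 36/44%, no effect): P(Yes) = 0.5387 and 0.5177. OR = (0.5387/0.4613)/(0.5177/0.4823) = 1.088, SE(log OR) = 0.0634, z = 1.33. Mean time on drug is 1.47 versus 1.39 years, about one month apart.

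Letting every patient run to 36 months gives larger values (OR 1.145, 55% rejection at 36/44%). That would produce 189 MACE, so it is only an upper bound.

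**Step 4, does the alternative help?** Data were simulated with a shared gamma frailty, 2-year accrual and assumed rates of 0.6 (moderate) and 0.4 (mild). At 36/44% with no effect, the logistic test rejects 25% (moderate) and 19% (mild), and Cox time to first event 4.9% and 4.5%. With a true 0.86, Cox has 73% and 68% power against 20% and 20% for logistic.

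**The case against.** The strongest reply is that nothing goes wrong on the SAP's own inputs. It gives one pooled discontinuation figure, and under equal stopping the test holds its level and keeps power. Every adverse number above needs an assumed imbalance. That is correct. A reader might infer that the plan expects or builds in a bias; it does not.

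Second, an imbalance would be seen. Section 4.2.1 plans a log-rank test of time to IP discontinuation, and section 4.2.3.1 reports exposure by arm. With about 1,450-1,470 discontinuations (0.2554 × 5,666 to 5,762 patient-years), power to flag 38/42% is about 70%, and over 99% for 36/44%. This stands, but seeing the imbalance does not correct the odds ratio.

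Third, section 4.2.4 treats CIs descriptively and confines the testing sequence to the primary and secondary variables. So the rejection rates measure how misleading the p-value could be, not an error rate the plan relies on.

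Three further limits stand:

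- The categories are patients with at least one mild, or at least one moderate, event, not patients with only such events.
- Exponential stopping from 40% at year 2 implies 22.5% at year 1, lighter than the 30% in section 1.3.2, so the figures are illustrative.
- The simulation treats severities as separate streams. Section 3.1.6 merges relapses within 7 days and assigns the worst severity.

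A reader might also see a contradiction between *whole study period* in section 1.2 (on plus off treatment) and the on-treatment default. Section 4.2.4.1 lists on-treatment and on-study analyses over the whole study as separate outputs, so this is editorial.

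**Conclusion.** The point holds as a low-priority improvement. The logistic model ignores time on drug, and for the mild and the moderate categories taken separately it is the only planned whole-study comparison of arms. The distortion is conditional: none under equal stopping, and an odds ratio of about 1.09 with no true effect, or about 0.94 in place of about 0.86 with a true rate ratio of 0.86, if 36% versus 44% are off drug at year 2. That split is an assumption, as are the accrual pattern and any single-severity rate.

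Two stronger readings are not supported. The exacerbation conclusions as a whole are not exposed, because any and moderate-or-severe events have exposure-aware analyses and severe events nearly do. No primary or secondary efficacy conclusion is at risk, because these variables lie outside the testing sequence.

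**What to change.** In section 4.2.4.3, extend the Cox and Kaplan-Meier time-to-first-event analysis already planned there to first mild and first moderate exacerbation (severe optional). Censor at IP discontinuation as in section 3.1.2, and use the severity derived after relapses are merged under section 3.1.6. Make this the between-arm comparison for those categories. Keep the number and percentage of patients as descriptive, and label any retained odds ratio as not adjusted for time on drug. As an editorial matter, say once that the period for these variables is on-treatment.

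The cost is SAP wording and two or three more runs, with no new data. It adds a few unadjusted supportive analyses, and it still assumes non-informative censoring at IP discontinuation. In a harsh assumed case with no true effect (30% background stopping in both arms, plus stopping at the first moderate or severe event in 10% of aclidinium and 30% of placebo patients), the simulated Cox test for mild events rejects 9.0%, against 59% for the logistic test. That is much better but not free of bias.
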